
 - Changes in the measurement of the TRLNI (ET: visits 1 and final). - Changes of corneal and conjunctival stains with lysmine green (ET: visits 1 and final). - Corneal and conjunctival staining changes with fluorescein (ET: visits 1 and final). - Conjunctival hyperemia changes (ET: visits 1 and final). 	
Safety variables:	

 - Incidence of unexpected AEs related to the research product. (ET: visits 1, final and evaluation) - Changes in the MAVC (ET: visits 1 and final). - Incidence of chemosis (ET: visits 1 and final). 	

Statistical methodology

The Kolmogorov-Smirnov and Shapiro Wilk tests will be performed, as appropriate, to know if the distribution presents normality in the results obtained in each study group. The data will be expressed with measures of central tendency: mean and standard deviation for the quantitative variables. Qualitative variables will be presented in frequencies and percentages. The statistical analysis will be performed by means of the analysis of variance test (ANOVA) for the quantitative variables for the difference between the groups. The difference between the qualitative variables will be analyzed by means of the χ^2 (*Chi-square*) or *Fisher's exact test*. A non-inferiority margin (δ) of 10% will be used for the OSDI score based on the primary endpoint of the study, a $\alpha \leq 0.05$ will be considered significant.

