1.3 Patient Timeline

The screening visit will correspond to an appointment that will be considered on day 0 for each patient. The baseline visit should be carried out 0 to 2 days after the scrutiny visit and can therefore be carried out on the same day as the latter.

Visit 1 will be carried out in relation to the start of treatment on day 17, with a window period of ± 1 day.

The final visit will take place on day 31 of the study, in relation to the start of treatment, with a window period of ± 1 day.

The safety call will be made 38 days after the start of treatment, with a window period of ± 1 day.

Procedures	SV	BV	V1	FV	SC
	D 0	D 0 to 2	D 1 to 3	D 17 to 1 (± 1)	D 31 to 33 (± 1)
					D 38 to 40 (± 1)
FCI Signature	X				
Medical history	X				
Concomitant Drug Evaluation	X			X	X
Urine pregnancy test	X				X
Vitals signs	X			X	X
BCVA	X			X	X
Ocular Surface Integrity (Stains and Evaluation of Hyperemia and Conjunctival Chemosis)	X			X	X
Comprehensive ophthalmological evaluation	X			X	X
OSDI	X			X	X
Eligibility Criteria	X	X			
AE´s Assessment	X	X		X	X
TBT		X		X	X
Investigational Product (PI) Randomization		X			
Delivery of the PI		X			
Delivery of patient material and filling instructions		X			
Start of intervention			X		
Adherence assessment				X	X
Patient Journal Return / Evaluation					X
Return of PI					X

Table 2. Patient schedule

2. Introduction and Background

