3.3 Hypothesis

H_0 = The Humylub Ofteno® PF ophthalmic solution is not inferior in its efficacy compared to its comparators, after 30 days of treatment, presenting a 35% decrease in the final score of the OSDI test compared to its initial value in at least 30% of exposed patients.

$$H_0: P_A - P_B \leq \delta$$

H_1 = The Humylub Ofteno® PF ophthalmic solution is inferior in its efficacy compared to its comparators, after 30 days of treatment, as it does not present a 35% decrease in the final score of the OSDI test compared to its initial value in at least 30% of exposed patients.

$$H_1: P_A - P_B > \delta$$

4. Study design

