7.4 Outcome variables

7.4.1 Primary outcome variables

- OSDI score (TE: visits 1 and final).

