7.4.4 Definition of variables, methods and scales to be used for the measurement

Variable	Conceptual Definition	Operational Definition	Measurement Type	Normal value	Statistical test
OSDI Score	OSDI is a questionnaire designed to establish a severity and Classification of dry eye according to its symptoms.	The evaluator will apply the questionnaire to the subject and allow the subject to answer it calmly without any pressure and/or coercion. See annex 16.1 OSDI .	Continuous quantitative	Score: OSDI= $\frac{\sum \text{score}}{25}$ n answers answered	
 • ANOVA of repeated measures. • One-way ANOVA*
TRLNI	Measurement of tear rupture time using non-invasive methods based on the observation of the film's mirror reflection in a grating design or in the placid discs of the corneal topographers and their analysis using specialized software.	The TRLNI will be measured by means of the Oculus Keratograph 5M.	Discrete quantitative	>10s	
 • ANOVA of repeated measures. • One-way ANOVA*
Corneal and conjunctival staining with lysmine green	Detection of epithelial defects in the conjunctiva and cornea.	Direct observation with slit lamp, graduation on Oxford scale. See annex 16.2 Oxford scale .	Ordinal Qualitative	Degrees: The stain is presented in a series of panels (A-E). The points Stains range from 0-5 for each panel and from 0-15 for the exposed toral area of the conjunctiva and cornea.	
 • χ^2 (Chi-square) of Pearson or Fisher's Exacta • McNemar Test*

Corneal and conjunctival staining with fluorescein	
Detection of epithelial defects in the conjunctiva and cornea.
	
Direct observation with slit lamp, graduation on Oxford scale. See annex 16.2 Scale of Oxford.
	
Ordinal Qualitative
	
Degrees: The stain is presented in a series of panels (A-E). The points Stains range from 0-5 for each panel and from 0-15 for the exposed toral area of the conjunctiva and cornea.
	
 • χ^2 (Chi-square) of Pearson or Fisher's Exacta • McNemar Test*

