10.1 Data analysis

10.1.1 Statistical Analysis

The statistical analysis will be carried out by personnel of Laboratorios Sophia, S.A. de C.V. The SPSS statistical package version 19.0 for Windows (IBM Corporation, Armonk, NY, USA) will be used. The coding will be done using consecutive numbers. The data will be collected and sorted in an Excel spreadsheet (Microsoft® Office). The data will then be exported to the SPSS package platform. The variables will be categorized according to their nature. See point 7.4.4 Definition of variables, methods and scales to be used for their measurement.

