10.1.2 Data Interpretation

The Kolmogorov-Smirnov and Shapiro Wilk tests will be performed, as applicable, to determine if the distribution of the data is normal in the results obtained in each study group [56].

The results of the continuous quantitative variables will be presented in measures of central tendency: mean, standard deviation, standard error and/or ranges.

- Intra-group analysis: For equal variances, Tukey's POST-HOC test will be used, otherwise the Dunnett statistic will be used. One-way analysis of variance (one-way ANOVA) will be used when applicable.
- Intergroup analysis: Differences between groups will be analyzed using the Repeated Measures Analysis of Variance (ANOVA) test or the Student's t-statistic when applicable.

A non-inferiority margin (δ) of 10% will be used for the primary efficacy endpoint, based on the primary endpoint of the study. The level of difference to consider significance will be an alpha (α) of 0.05 or less.

The result of the nominal and ordinal qualitative variables will be presented in frequencies, proportions and/or percentages.

The statistical analysis to identify significant differences in the qualitative variables will be carried out by creating 2x2 contingency tables and will be carried out as follows:

- Intra-group difference: McNemar test. This is applied to 2x2 contingency tables with a dichotomous feature, with pairs of paired subjects, to determine if the marginal frequencies of row and column are equal (marginal homogeneity) [7].

- Difference between groups: Pearson's X² (Chi-square) test or Fisher's exact test at expected values less than 5.

The level of difference to consider significance will be an alpha (α) of 0.05 or less.

For the reporting of adverse events, all subjects who were randomly assigned to an intervention group after baseline (intention-to-treat population, ITT) will be considered.

The final report of the results will be shown in tables or graphs, as appropriate.

Variable Type	Variable	A1	B1	B2	C1	D1	D2	D3	D4	E1	E2
Background											
A1	Demographic	DT									
Basal											
B1	Medical History/Selection Criteria	DT									
B2	Comprehensive ophthalmological evaluation	DT				TB	T	T	T	TB	TB
Efficiency											
C1	OSDI	DB			B					TB	
Secondary efficacy outcome											
D1	TRLNI				DB	B				TB	
D2	Corneal and conjunctival stains (TVL and TF)		DT	DT			TB			TB	
D3	Conjunctival Hyperemia		DT	DT		TB				TB	
D4	Chemosis		DT	DT		TB				TB	
Safety											

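### The between-arm test for OSDI, TRLNI and acuity fixes no effect, visit or missed-visit rule; repeated-measures ANOVA in its standard form drops incomplete patients and averages over visits, and a mixed model with a day-31 contrast avoids both

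*Combined protocol and SAP*

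**What the plan says.** - Section 10.1.2, intergroup analysis: "Differences between groups will be analyzed using the Repeated Measures Analysis of Variance (ANOVA) test". The sentence goes on to offer Student's t as an alternative, without defining when that applies. The same section places one-way ANOVA under the intra-group analysis.
- Section 7.4.4 lists "ANOVA of repeated measures" first for OSDI, TRLNI and acuity. One-way ANOVA comes second, with an asterisk that McNemar's test also carries.
- The Synopsis (1.2) says only "analysis of variance test (ANOVA) for the quantitative variables for the difference between the groups", with no type of ANOVA and no time point.
- Section 7.4.1 gives the primary variable as "OSDI score (TE: visits 1 and final"). Section 1.3 says "Visit 1 will be carried out in relation to the start of treatment on day 17" and puts the final visit on day 31, each with a window of one day either side. OSDI is also taken at screening.
- Section 3.3 frames the hypothesis at one time: "after 30 days of treatment, presenting a 35% decrease in the final score of the OSDI test compared to its initial value". The share of patients who must reach this is 30% or more.
- Section 10.1.3, headed as the procedure for missing data, covers the safety population only.
- Section 10.1.1 names the software: "The SPSS statistical package version 19.0 for Windows".

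**The concern.** Repeated-measures ANOVA in SPSS normally takes one row per patient and deletes any row with a gap. A patient who missed visit 1 but attended on day 31 would drop out of the comparison, although the score that matters was measured. A patient with a visit-1 score and no final score would contribute nothing. With no efficacy rule for missing data, the software default decides.

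The group main effect of that ANOVA is also the arm difference averaged over the visits entered. Randomised arms have an expected baseline difference of zero, so including baseline shrinks the estimate. In a superiority trial shrinkage costs power. Here it moves the result towards no difference, which is the direction of the sponsor's claim.

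**Working it through.** **What the plan supplies.** The only related figure is the arm size. Section 10.2.2 gives 50 per arm, and 50 × 1.2 = 60. The 50 reproduces if 49.3% and 35% are entered as proportions with a 10% margin at one-sided 0.05: (0.493×0.507 + 0.35×0.65) × ((1.645 + 0.842)/(0.493 − 0.35 + 0.10))² = 49.99. Whether those inputs are suitable is a separate matter. The calculation uses proportions, so the plan gives no OSDI standard deviation, no correlation between visits and no rate of missed visits. All three are assumed below.

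**1. Day-31 scores dropped.** Let *m* be the share missing visit 1 and *f* the share missing the final visit, independently. Scores dropped per arm = 60 × (1 − *f*) × *m*. For *f* from 0 to 20%:

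| Missing visit 1 | Day-31 scores dropped per arm |
|---|---|
| 0% | 0 |
| 2% | about 1 |
| 5% | 2.4 to 3 |
| 10% | 4.8 to 6 |
| 15% | 7.2 to 9 |

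With *m* = *f* = 10%, two arms (120 patients) have 108 day-31 scores and 97.2 complete rows, so 10.8 scores are dropped.

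**2. Averaging.** Let *r* be the visit-1 difference divided by the day-31 difference, with baseline difference 0. The main effect as a share of the day-31 difference is (0 + *r* + 1)/3 over three visits, or (*r* + 1)/2 over visit 1 and final only.

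| *r* | Baseline, visit 1, final | Visit 1, final |
|---|---|---|
| 0 | 33% | 50% |
| 0.5 | 50% | 75% |
| 1 | 67% | 100% |

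A simulation with true differences of 0.25 SD at visit 1 and 0.50 SD at day 31, 60 per arm and no missing data, gave a mean main effect of 0.251 SD (standard error 0.149) and a day-31 contrast of 0.501 SD (standard error 0.183). Estimate over standard error is 0.251/0.149 = 1.68 against 0.501/0.183 = 2.74. Averaging halves the effect and narrows the error by less, so a real day-31 difference is harder to see.

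**3. Precision of the day-31 change contrast.** Assume 60 per arm, SD 10, 15% without a final score, 10% missing visit 1, and correlations of 0.6 (baseline with visit 1), 0.7 (visit 1 with final) and 0.5 (baseline with final).

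- Complete rows: 60 × 0.85 × 0.90 = 45.9 per arm. Variance = 2 × 100 × 2(1 − 0.5)/45.9 = 4.357, SD 2.09.
- All available day-31 changes: 60 × 0.85 = 51 per arm. Variance = 200/51 = 3.922, SD 1.98.
- Maximum likelihood on all visits: 2c′I⁻¹c, where c = (−1, 0, 1) and I is the sum over missing-data patterns of the number of patients times the inverse covariance of the visits observed. Variance = 3.640, SD 1.91.

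The ratios to maximum likelihood are 4.357/3.640 = 1.20 and 3.922/3.640 = 1.08. Over correlations from 0.5 to 0.7, and whether or not the two kinds of miss overlap, they run from 1.16 to 1.23 for complete rows and 1.04 to 1.08 for all available changes. Simulation with the covariance estimated gave SDs of 2.14, 2.04 and 1.96, consistent with this. Central values are about 18% and 7%.

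As a cross-check with baseline adjustment and equal correlations of 0.3 to 0.7, complete-row standard errors exceed those of the mixed model by 3–4% at 5% missing visit 1 and by 5–7% at 10%. A day-31-only ANCOVA is within 0–2% of the mixed model.

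**4. Bias.** If dropout in one arm rises with visit-1 OSDI, simulated complete-row bias ranged from about −0.1 to −0.5 point depending on the dropout strength and correlations assumed, against 0 to −0.1 with maximum likelihood. The largest value is about 0.46/2.14 = 0.2 of a standard error.

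**The case against.** The plan does not commit itself to the harmful version. The sentence in 10.1.2 continues to Student's t, and a t-test on the final visit keeps every day-31 score. One-way ANOVA at the final visit would do the same, but that route is weaker: 10.1.2 assigns one-way ANOVA to the intra-group analysis, and its asterisk in 7.4.4 is shared with McNemar's test, also intra-group. If the two labels in 10.1.2 were exchanged by mistake, the text does not say so.

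Averaging affects the group main effect only. The arm-by-visit term, or a final-visit contrast from the same ANOVA, does not average. Section 7.4.1 names both visits, so using both is not in itself an error.

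A reader might take the 20% loss allowance as the size of the problem. It is not. Section 5.6 defines loss to follow-up as a final evaluation that could not be completed, so those patients have no day-31 score to discard. The same section provides for rebooking a missed appointment, and 5.5 expects no retention problems. Few patients may miss visit 1 alone, and at 2% about one score per arm is lost.

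A reader might also credit the mixed model with the whole 18%. More than half of that gain comes from simply using every day-31 change.

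These points stand and limit the size. They do not remove the gap: no section says which test, effect or visit is primary for the continuous variables, or what happens to a patient with a missed visit.

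**Conclusion.** The point holds as an unguarded choice, not as a certain loss of data. Repeated-measures ANOVA is the first-named between-arm test. If it is run in its standard SPSS form and the group main effect is read, patients with any missed visit are dropped and a day-31 difference is diluted to between one third and two thirds of its size when baseline is included (visit-1 difference between none and all of the day-31 difference). The dilution is the more serious part, because it favours a non-inferiority conclusion.

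The precision cost is moderate and rests on assumed rates: about 18% more variance than maximum likelihood with complete rows, and about 7% with a simple day-31 change comparison. Bias from dropout that depends on visit 1 is at most a few tenths of an OSDI point under the assumptions tried, and the documents give no reason to expect such dropout to differ by arm.

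It would be wrong to infer that a mixed model settles the primary hypothesis. Sections 3.3 and 10.2.2 concern a proportion of responders and a 10% margin, and an analysis of mean OSDI gives no estimate of that difference.

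**What to change.** In 10.1.2 and the table in 7.4.4, for the continuous analyses of OSDI, TRLNI and acuity, replace repeated-measures ANOVA by a linear mixed model (SPSS MIXED):

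- fixed effects for arm, visit and arm-by-visit;
- all available visits of each patient in the analysis set, with no deletion for a missed visit;
- unstructured covariance over visits within patient and, for the per-eye measures, an added term for the two eyes of one patient;
- prespecified day-31 contrasts, Humylub minus Hyabak and Humylub minus Lagricel, each with a confidence interval.

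Add to 10.1.3 that these efficacy analyses use all observed visits under this model. State separately how the day-30 responder proportion will be compared with the 10% margin; the model does not replace that analysis.

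The cost is a revised paragraph and a little more programming in the package already named. No new data are needed.

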H_1 = The Humylub Ofteno® PF ophthalmic solution is inferior in efficacy to its comparators after 30 days of treatment, as it does not show a 35% decrease in the final OSDI test score from baseline in at least 30% of exposed patients.
$H_1: P_A - P_B > \delta$
Study design:
Phase IV non-inferiority, controlled, open-label, comparative, multicenter clinical trial.
Number of subjects (planned and analyzed):
Number of patients planned: 60 evaluable patients per arm. Total sample = 180 evaluable patients.
Diagnosis and main inclusion criteria:

 - Patients diagnosed with mild to moderate dry eye.
Selection criteria:
Inclusion criteria:

 - Can voluntarily give their signed informed consent. - Be able and willing to comply with scheduled visits, treatment plan, and other study procedures. - Be of legal age. - Women of childbearing potential must ensure the continuation (initiated ≥ 30 days prior to signing the informed consent form [ICF]) of the use of a hormonal contraceptive method or intrauterine device (IUD) during the study period. - Present a diagnosis of mild to moderate dry eye, defined by an OSDI rating ≥ 13 and one of the following: 
 o Corneal staining with more than 5 sites.

- Conjunctival staining with more than 9 sites.
- Tear film breaking time < 10 seconds.

Exclusion criteria:

[figure not shown]
- Women who are pregnant, breastfeeding, or planning to become pregnant within the study period.
- Have participated in another clinical research study ≤ 30 days prior to the screening visit.
- Have previously participated in this study.
- Have a CVAM of 20/200 or worse in one of the eyes.
- Present an ophthalmological diagnosis of:
 - Allergic, viral, or bacterial conjunctivitis.
 - Blefaritis anterior.
 - Parasitic infestations in any ocular structure or its appendages.
 - Unresolved eye trauma.
 - Healing diseases of the ocular surface.
 - Corneal or conjunctival ulcers.
 - Filamentous keratitis.
 - Neurotrophic keratitis.
 - Bullous keratopathy.
 - Neoplastic diseases on the ocular surface or adnexa.
 - Diseases with fibrovascular proliferations on the conjunctival and/or corneal surface.
 - Retinal and/or posterior segment diseases that require treatment or threaten visual prognosis.
 - Glaucoma.
 - Disorders of the eyelids that cause palpebral malpositions, limit the proper closing or opening of the eyelids, or are the cause of epiphora.

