7.5.1.2 Basal Visit

- Eligibility criteria: refers to the review by the PI, where it is found that the patient can be included in the study by meeting the inclusion criteria and not meeting the exclusion criteria.
- Evaluation of AEs: see section 7.4.4.1 Adverse events.
- TRLNI: see point 7.4.4.4 TRLNI.

- IP randomization: refers to determining the intervention that the patient will follow during the study. This assignment will be made at baseline visit (day 0). See point 7.3 Randomization
- Delivery of the PI and initiation of intervention refers to the delivery of the PI to the study patient, by the research center.
- Delivery of patient material and filling instructions refers to the delivery by the PI to the patient of the patient's diary, ID card and calendar improving adherence. The staff assigned by the research center will carry out prior training to the patient, on the completion of the diary.

7.5.1.3 Visit 1

- Evaluation of concomitant medications: see point 7.5.1.1 Screening Visit.
- Vital signs: refers to the measurement of heart rate, respiratory rate, systemic blood pressure and temperature. This information must be contained in the patient's medical history and the evolution notes of the patient's clinical file.
- OSDI: see section 7.4.4.2 OSDI score.
- CVAM: see section 7.4.4.3 Better corrected visual acuity.
- TRLNI: see point 7.4.4.4 TRLNI.
- Ocular surface stains: see points 7.4.4.5 Corneal and conjunctival staining with fluorescein and 7.4.4.6 Conjunctival staining with lysmine green.
- Comprehensive ophthalmological evaluation: see point 7.4.4.1 Adverse events.
- Evaluation of AEs: see section 7.4.4.1 Adverse events.
- Evaluation of adherence: see point 7.5.1.1 Scrutiny visit.

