E1	Incidence of AD				TB	TB	TB	TB	TB	TM	
E2	MAVC		DB							TM	B

D, Descriptive Statistics; T, 2x2 contingency table; B, Bivariate Analysis; M, Multivariate Analysis.

Table 3. Triangulation of concepts

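### The OSDI and TRLNI comparisons name no baseline covariate and leave baseline's role in the repeated-measures model unstated; prespecifying adjustment is a nearly free gain in precision

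*Combined protocol and SAP*

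**What the plan says.** Section 10.1.2 states the between-arm method for continuous outcomes: "Differences between groups will be analyzed using the Repeated Measures Analysis of Variance (ANOVA) test", with Student's t as the alternative where it applies. The variable table in 7.4.4 gives OSDI and TRLNI "ANOVA of repeated measures" plus one-way ANOVA. The Synopsis is more general: "The statistical analysis will be performed by means of the analysis of variance test (ANOVA) for the quantitative variables for the difference between the groups". Section 10.1.2 lists one-way ANOVA under within-group analysis, whereas the Synopsis uses ANOVA between groups, so which test is the between-arm one is itself loosely stated.

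No section names ANCOVA or a baseline covariate for either outcome. Table 3 uses the key "D, Descriptive Statistics; T, 2x2 contingency table; B, Bivariate Analysis; M, Multivariate Analysis". Its OSDI and TRLNI rows carry only D, T and B codes, and M appears only in the two safety rows (adverse events and visual acuity).

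The baseline data exist. Entry requires dry eye "defined by an OSDI rating ≥ 13 and one of the following" objective signs, and OSDI is done at screening (7.5.1.1). The baseline visit lists "TRLNI: see point 7.4.4.4 TRLNI" ahead of randomisation (7.5.1.2). Section 7.4.1 gives visit 1 and the final visit as the OSDI time points. Section 7.4.2 defines the TRLNI outcome as a change.

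**The concern.** A pre-randomisation measurement of the same outcome usually explains part of the variation in the final measurement. Leaving it out of the model widens the confidence interval and leaves chance baseline imbalance in the estimate. With about 50 evaluable patients per arm, neither effect is negligible.

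The plan is also open on a point that changes the result. Repeated-measures ANOVA could have visit 1 and the final visit as its levels, with baseline absent, or could have baseline as a third level. In the second case the test could be the group main effect or the group-by-time term. These analyses differ in power, and no model term is named. A choice made after the data are seen is harder to defend than one fixed in advance.

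**Working it through.** **Inputs from the documents.** 50 evaluable patients per arm, raised by 20% to 60 (10.2.2); equal allocation; baseline OSDI and TRLNI collected before randomisation.

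**Inputs assumed.** The documents give neither the baseline-final correlation r nor the SD. I take r = 0.3, 0.5 and 0.7, equal variances over time and, for the formulas, one post-baseline visit.

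**The plan's own figure.** The formula printed in 10.2.2, with 30% response in both arms (the comparator rate is not stated, so equality is assumed), δ = 0.10, one-sided 0.05 and 80% power, gives (0.21 + 0.21) × ((1.645 + 0.842)/0.10)² ≈ 260 per arm, not 50. That is a separate and larger matter. It is shown so that nobody expects a covariate to close the gap.

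**Variance of the between-arm mean difference, with final-score analysis set to 1.** Change score: 2(1 − r). ANCOVA: 1 − r². The ratio of ANCOVA to change score is (1 − r²)/(2(1 − r)) = (1 + r)/2.

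| r | Change score | ANCOVA | ANCOVA/change | Cut vs final score | Cut vs change score | 50 per arm is worth, vs final / vs change |
|---|---|---|---|---|---|---|
| 0.3 | 1.40 | 0.91 | 0.65 | 9% | 35% | 55 / 77 |
| 0.5 | 1.00 | 0.75 | 0.75 | 25% | 25% | 67 / 67 |
| 0.7 | 0.60 | 0.51 | 0.85 | 49% | 15% | 98 / 59 |

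The last column is 50/(1 − r²) and 50 × 2/(1 + r).

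**Chance imbalance.** With 50 per arm, the standard error of a baseline mean difference is √(2/50) = 0.2 SD, so a difference of about 0.4 SD (1.96 × 0.2) is within ordinary chance. At r = 0.5 it moves a final-score comparison by 0.5 × 0.4 = 0.2 SD and a change-score comparison by (0.5 − 1) × 0.4 = −0.2 SD.

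**Repeated-measures options.** I used a simulation of 4,000 trials per setting: two arms of 50, three visits, the same correlation r between all visits, a true difference of 0.5 SD at both post-baseline visits, and two-sided 0.05. It gave this power:

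| Analysis | r = 0.3 | r = 0.5 | r = 0.7 |
|---|---|---|---|
| Final score only | 0.69 | 0.69 | 0.70 |
| Change score | 0.56 | 0.69 | 0.89 |
| Group main effect, baseline as a level | 0.60 | 0.51 | 0.45 |
| Group-by-time, baseline as a level | 0.57 | 0.73 | 0.93 |
| ANCOVA on final visit | 0.73 | 0.80 | 0.93 |

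The group main effect with baseline as a level does poorly because it averages in a visit at which no treatment difference can exist. The group-by-time test matches ANCOVA at r = 0.7 and falls behind it at lower r. This is power to detect a mean difference, not power for the non-inferiority test.

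**The case against.** A reader might infer that the plan ignores baseline altogether. The documents do not support that. Baseline may be a level in the repeated-measures model, in which case a group-by-time test compares changes from baseline. TRLNI is defined as a change, so baseline is already subtracted. The hypothesis in 3.3 judges response against the initial OSDI value. What stands is narrower: baseline is not a covariate anywhere, and its place in the repeated-measures model is not stated.

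A reader might also infer that the variance cuts carry straight into the non-inferiority decision. They do not. The hypotheses and the formula in 10.2.2 apply δ to a difference in responder proportions. The Synopsis attaches the 10% to the OSDI score, but no margin in OSDI points is given. No figure is available for what adjustment gains on the responder difference.

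The size of the gain is open too. It rests on an assumed r. The entry criterion sets a floor of 13 and no ceiling, yet the population is called mild to moderate and 7.4.4.2 classes 33 and above as severe. The baseline spread, and with it r, could therefore be wide or narrow. The documents do not show that baseline strongly predicts the final score.

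Finally, randomisation makes the unadjusted tests valid. Chance imbalance in a single trial is noise, not bias. That objection stands in full and sets the weight of the point.

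**Conclusion.** The point holds as an efficiency improvement at almost no cost. No baseline covariate is planned for OSDI or TRLNI, and both baselines will be in hand. For r between 0 and 1, ANCOVA is at least as precise as a final-score or change-score analysis, apart from the one degree of freedom spent on the covariate. Under the assumed r of 0.3 to 0.7 with one post-baseline visit, the variance of the mean difference falls by 9% to 49% against final score and by 35% to 15% against change score. Against a group-by-time test with baseline as a level, the gain ranges from clear at r = 0.3 to about nil at r = 0.7.

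The conclusion goes no further than that. The planned tests are not wrong. Adjustment does not rescue the stated sample size, and it does not resolve the mismatch between tests on means and a hypothesis about responders.

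**What to change.** - For OSDI and TRLNI, prespecify ANCOVA of the final-visit score on arm and baseline score, or a longitudinal model with baseline as covariate. Report the adjusted difference with its confidence interval for each of the two comparators.
- Set one rule for the baseline covariate, for example the last value before randomisation. The text closing 7.5.1.1 now lets the investigator use either the screening value or a repeat at the baseline visit.
- For TRLNI, allow for two eyes per patient (10.2.2 has both eyes contributing) by a patient-level mean or a within-patient correlation term.
- For the 35% responder endpoint, report a baseline-adjusted standardised risk difference, for example from a logistic model with baseline OSDI, with its confidence interval set against the margin read as 10 percentage points. Claim no specific precision gain.

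The cost is SAP wording, including the baseline and both-eyes rules. No new data, visits or patients are needed.
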